16.3.1 Amendments

Each change to the protocol document must be organized and documented by MSK and first approved by the MSK IRB/PB. Upon receipt of MSK IRB/PB approval, MSK will immediately distribute all non expedited amendments to the participating sites, for submissions to their local IRBs.

Participating sites must obtain approval for all non expedited amendments from their IRB within 90 calendar day of MSK IRB/PB approval. If the amendment is the results of a safety issue or makes eligibility criteria more restrictive, sites will not be permitted to continue enrolling new participants until the participating site IRB approval has been granted.

The following documents must be provided to MSK for each amendment within the stated timelines:

- Participating Site IRB approval
- Participating Site IRB approved informed consent form and HIPAA authorization

16.3.2 Additional Correspondence

Continuing Review Approval

The Continuing Review Approval letter from the participating site's IRB and the most current approved version of the informed consent form should be submitted to MSK within 7 days of expiration. Failure to submit the re-approval in the stated timeline will result in suspension of new participant enrollment.

16.4 Document maintenance

The MSK PI and participating site PI will maintain adequate and accurate records to enable the implementation of the protocol to be fully documented and the data to be subsequently verified.

The participating sites will ensure that all regulatory documents and participating site IRB correspondences are maintained in an on site regulatory binder and sent to MSK as outlined within the protocol. The regulatory binder on site will be reviewed by the MSK designated study monitor at monitoring visits. A regulatory binder for each site will also be maintained at MSK this binder may be paper or electronic.

After study closure, the participating sites will maintain all source documents, study related documents and CRFs for 3 years.

16.5 Noncompliance

If a participating site is noncompliant with the protocol document, accrual privileges may be suspended and/or contract payments may be withheld, until the outstanding issues have been resolved.

17.0 PROTECTION OF HUMAN SUBJECTS

Inclusion of Children in Research

This protocol/project does not include children because the number of children is limited and the majority are already accessed by a nationwide pediatric cancer research network. This statement is based on exclusion 4b of the NIH Policy and Guidelines on the Inclusion of Children as Participants in Research Involving Human Subjects.

Incentives/Costs/Benefits

No incentives will be offered to patients/subjects for participation in this study. Participation is voluntary. The potential benefits of participation in the study will be weighed against other treatment options (see below) including supportive care. The patient/subject or their health insurance provider will be responsible for the costs of standard medical care including MD visits, routine blood tests, administration of the study drug, and bone marrow biopsies and aspirates. The patient/subject or their health insurance provider will not be charged for the study drug romiplostim.

Alternative Treatments: N/A

Alternative treatment of patients: Usual care with delay or dose reduction in chemotherapy.

17.1 Privacy

MSKCC's Privacy Office may allow the use and disclosure of protected health information pursuant to a completed and signed Research Authorization form. The use and disclosure of protected health information will be limited to the individuals described in the Research Authorization form. A Research Authorization form must be completed by the Principal Investigator and approved by the IRB and Privacy Board (IRB/PB).

17.2 Serious Adverse Event (SAE) Reporting

SAE reporting is required as soon as the participant signs consent. SAE reporting is required for 30-days after the participant's last investigational treatment or intervention. Any events that occur after the 30-day period and that are at least possibly related to protocol treatment must be reported.

If an SAE requires submission to the IRB office per IRB SOP RR-408 'Reporting of Serious Adverse Events', the SAE report must be sent to the IRB within 5 calendar days of the event. The IRB requires a Clinical Research Database (CRDB) SAE report be submitted electronically to the SAE Office as follows:

For all other trials: Reports that include a Grade 5 SAE should be sent to [contact]. All other reports should be sent to [contact].

The report should contain the following information:

Fields populated from CRDB:

- Subject's initials
- Medical record number
- Disease/histology (if applicable)
- · Protocol number and title

Data needing to be entered:

- The date the adverse event occurred
- The adverse event
- The grade of the event
- Relationship of the adverse event to the treatment (drug, device, or intervention)
- If the AE was expected
- The severity of the AE
- The intervention
- Detailed text that includes the following

- A explanation of how the AE was handled
- A description of the subject's condition
- Indication if the subject remains on the study
- If an amendment will need to be made to the protocol and/or consent form
- If the SAE is an Unanticipated Problem

The PI's signature and the date it was signed are required on the completed report.

17.2.1 Report SAEs to Amgen by MSKCC

The MSKCC research staff must inform Amgen, Inc. of any SAE as soon as possible but no later than 5 calendar days of the MSKCC principal investigator becoming aware of the event. Participating sites should submit SAEs to MSKCC as indicated in section 17.3 and MSKCC will report these events to Amgen as appropriate. Participating sites should not submit SAEs directly to Amgen. All SAE's will be reported up to 30 days after the last dose of treatment.

Definitions

Adverse Event Definition

Adverse event (AE) means any untoward medical occurrence(s) in a patient/subject attributed to a pharmaceutical product. (The untoward medical occurrence does not necessarily have a causal relationship with this treatment.) An AE can therefore be any unfavorable and unintended sign (including an abnormal laboratory finding), symptom, or disease temporally associated with the use of a medicinal (investigational) product whether or not it is related to the medicinal product. This includes any newly occurring event, or a previous condition that has increased in severity or frequency since the administration of study drug.

Serious Adverse Event Definition

Serious adverse event (SAE) means any untoward medical occurrence that at any dose:

- Results in death.
- Is life-threatening (refers to an AE in which the patient was at risk of death at the time of the event. It does not refer to an event which hypothetically might have caused death if it were more severe).
- Requires inpatient hospitalization, with the exception of a planned procedure.
- Requires prolongation of an existing hospitalization.
- Results in persistent or significant disability or incapacity. (Disability is defined as a substantial disruption of a person's ability to conduct normal life functions).
- Is a congenital anomaly/birth defect.
- Is a medically important event. This refers to an AE that may not result in death, be immediately life threatening, or require hospitalization, but may be considered serious when, based on appropriate medical judgment, may jeopardize the patient, require medical or surgical intervention to prevent one of the outcomes listed above, or involves suspected transmission via a medicinal product of an infectious agent.

Clarification should be made between the terms *serious* and *severe* because they ARE NOT the same. The term *severe* is often used to describe the intensity (severity) of a specific event (as in mild, moderate, or severe myocardial infarction); the event itself, however, may be of relatively minor medical significance (such as a severe headache). This is NOT the same as *serious*, which is based on patient/event outcome or action criteria described above and is usually associated with events that pose a threat to a patient's life or functioning. A severe AE does not necessarily need to be considered serious. For example, persistent nausea of several hours duration may be considered severe nausea but may not be considered an SAE. On the other hand, a stroke resulting in only a minor degree of disability may be considered mild but would be defined as an SAE based on the above noted criteria. Seriousness (not severity) serves as a guide for defining regulatory reporting obligations.

17.3 SAE Reporting for Participating Sites

Responsibilities of Participating Sites

- Participating sites are responsible for reporting all SAEs to their local IRB per local guidelines. Local IRB SAE approvals/acknowledgements must be sent to MSK upon receipt.
- Participating sites are responsible for submitting the SAE Report form found in MSK's internet based Clinical Research Database to MSK within 3 calendar days of learning of the event.
- When a death is unforeseen and indicates participants or others are at increased risk of harm, participating sites should notify the MSK PI as soon as possible but within 24 hours of the time the site becomes aware of the event.

SAE contact information:

Email: [contact] to the attention of 13-132 Research Staff

AND

Email: [contact]

Responsibilities of MSK

- MSK Research Staff are responsible for submitting all SAEs to the MSK IRB/PB as specified in 17.2 and to Amgen as described in 17.2.1
- The MSK PI is responsible for informing all participating sites about all unexpected SAEs that are either possibly, probably, or definitely related to the study intervention within 30 days of receiving the stamped SAE from the MSK IRB/PB
- The MSK PI is responsible for informing all participating sites within 24 hours or on the next business day about a death that is unforeseen and indicates participants or others are at increased risk of harm.

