4.0 OVERVIEW OF STUDY DESIGN/INTERVENTION

4.1 Design

Primary objective:

This is an intent-to-treat multicenter phase II open label trial. Once appropriate patients are identified and enrolled, 60 patients will be enrolled.

During the initial 3-week period, the enrolled patients will receive romiplostim, titrated as per protocol (Section 9.0). Assessment for the primary endpoint will take place at week 3 and denote the proportion of patients that achieves a platelet count of >100,000/mcL within 3 weeks of initiation.

Safety Analysis will be performed at specified time-points (Section 11.0 Toxicities/Side Effects) including possible adverse events such as thrombosis, peripheral blood abnormalities and evidence of organ dysfunction.

Secondary objective:

In patients whose platelet counts have recovered within three weeks, we will observe for patient's ability to receive two cycles (or eight weeks, whichever comes first) of cytotoxic chemotherapy without recurrence of chemotherapy-induced thrombocytopenia leading to chemotherapy dose delay or reduction; change in chemotherapy for progression of disease or other cancer related conditions; change in chemotherapy for other toxicities unrelated to thrombocytopenia; and death due to all causes. The duration for patients off-chemotherapy will also be noted. In addition we are also censoring patients who have tolerated chemotherapy with romiplostim support for up to 12 months.

Safety endpoints will include possible adverse events such as thrombosis, evidence of marrow toxicity, and evidence of organ dysfunction.

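### Non-fatal, unexpected SAEs possibly related to romiplostim may reach the other sites as late as 30 days after an IRB stamp that has no time limit, although the manufacturer must be told within 5 days of PI awareness

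*Combined protocol and SAP*

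**What the plan says.** Section 17.3, under the responsibilities of MSK, makes the MSK PI responsible for "informing all participating sites about all unexpected SAEs that are either possibly, probably, or definitely related to the study intervention". The time allowed is "within 30 days of receiving the stamped SAE from the MSK IRB/PB". The next bullet sets a faster rule, 24 hours or the next business day, for a death that is unforeseen and signals increased risk to participants or others.

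Three other clocks bear on the same event:

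- **Site to MSK (Section 17.3):** the SAE form is due "within 3 calendar days of learning of the event".
- **MSK to the IRB (Section 17.2):** "the SAE report must be sent to the IRB within 5 calendar days of the event". This applies under a condition: "If an SAE requires submission to the IRB office per IRB SOP RR-408".
- **MSK to the manufacturer (Section 17.2.1):** any SAE, "as soon as possible but no later than 5 calendar days of the MSKCC principal investigator becoming aware of the event".

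The documents do not say how long the IRB may take between receiving a report and returning it stamped.

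**The concern.** The clock for telling the other treating sites does not start when MSK learns of the event. It starts when the IRB returns a stamped report, a step outside the investigators' control and without a stated limit, and it then allows 30 days. The manufacturer, which treats no trial patient, hears on a 5-day clock that starts at PI awareness. An event that was life-threatening but not fatal, unexpected and judged possibly related would go to the sites by the slower route.

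At stake is what the other sites know while they go on treating. Romiplostim is given weekly (Section 9.0), and Section 4.2 lets patients who benefit stay on it beyond 12 months. Investigators and treating oncologists use judgment about continuation after adverse events (Sections 9.0, part III, and 13.0), and Section 18.0 requires risks to be explained at consent. Under the rule as written, these steps can proceed without information that MSK already holds and has sent to the manufacturer.

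**Working it through.** The plan states no overall time to notification, so there is no figure to reproduce. The check is calendar arithmetic on the stated limits, followed by a search for a faster route.

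**Inputs**

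- Event to IRB: at most 5 days (17.2), where submission is required.
- IRB submission to stamp: not stated. Call it *s* days; I assume 0 to 30 to show the range.
- Stamp to notice at the other sites: at most 30 days (17.3).
- Site learning of the event to MSK: at most 3 days (17.3).
- MSK PI awareness to manufacturer: at most 5 days (17.2.1).
- Dosing: weekly (9.0).

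**Latest notice to the other sites, counted from the event**

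5 + *s* + 30 = 35 + *s* days.

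| Assumed *s* (days) | Notice due by day | Weekly intervals (days / 7) |
|---|---|---|
| 0 | 35 | 5 |
| 7 | 42 | 6 |
| 14 | 49 | 7 |
| 30 | 65 | 9.3 |

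The last column assumes uninterrupted weekly dosing.

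**Latest notice to the manufacturer**

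For an event at a participating site: 3 + 5 = 8 days, counted from the site learning of it. That is a different start from the 35 + *s* days. To align the two, assume that the site learns on the day of the event and that the MSK PI becomes aware when the site's report falls due. The gap is then (35 + *s*) − 8 = 27 + *s* days. Each day that the site learns later takes one day off this gap. For an event at MSK known to the PI the same day, the gap is (35 + *s*) − 5 = 30 + *s* days.

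**Is there a faster route for a non-fatal event in this trial?**

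- *17.3, 24-hour rule:* deaths only.
- *17.5:* external safety reports, with an alert if one requires an amendment. It does not address events arising in this trial.
- *16.3.1:* non-expedited amendments go out promptly once approved, and a safety amendment halts a site's enrolment until its own IRB approves. This helps only after an amendment has been written and approved.
- *16.2:* committee oversight of the trial, with no duty to notify sites of an event.

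None of these fills the gap.

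**Can the clock fail to start?** Section 17.2 makes IRB submission depend on an institutional procedure that is not reproduced. Section 17.3 speaks of submitting all SAEs, but as specified in 17.2. If an event needed no submission, there would be no stamp from which to count the 30 days. This is an ambiguity in the text, not a demonstrated failure.

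**The case against.** **Ceiling, not practice.** The 30 days is a maximum, and MSK may notify sooner. The site where the event occurred already knows, and Section 9.0 discontinues romiplostim for a Grade 3/4 event attributed to it. This stands: the figures above are upper bounds and concern the other sites only. But the maximum is all that the plan commits to.

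**No contradiction.** A reader might infer that Sections 17.2.1 and 17.3 conflict. They do not. The manufacturer receives every SAE unfiltered, while sites receive a subset after IRB processing, and different recipients and content can have different clocks. The comparison shows only that a 5-day clock is already being run for the same events.

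**Not all serious hazards.** A reader might infer that every unexpected related SAE waits for the stamp. The 24-hour rule for certain deaths shows otherwise, so the point is confined to non-fatal events.

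**Not an endpoint problem.** Section 4.1 says "Assessment for the primary endpoint will take place at week 3", and 30 days exceeds 21, so it is tempting to argue that patients would be scored before their site is warned and that the result suffers. The documents do not support that. Three weeks is the efficacy window, not a limit on exposure; the endpoint is a platelet count; and nothing shows how late notice of another patient's SAE would shift it. Section 14.0 also reports 61 patients enrolled for 60 spots, so few or none may still be due to enter that window. Patients on maintenance remain exposed.

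**Local decisions concern the patient's own event.** The continuation rules in Sections 9.0 and 13.0 are not written to depend on SAEs elsewhere. That is right; the argument is only that such judgments are better made with known safety information.

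**Unseen material.** The contents page lists a multicenter addendum, and Section 17.2 cites an IRB procedure; neither is in the text available. Either might limit the stamp time or add a rule on notifying sites.

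**Conclusion.** The point holds for non-fatal, unexpected SAEs at least possibly related to romiplostim. Followed as written, Section 17.3 lets notice to the other sites fall due up to 35 days after the event plus an unstated stamp time: 35 to 65 days if the stamp takes 0 to 30 days. With the clocks aligned as above, that is 27 + *s* days after the manufacturer's deadline for an event at a participating site.

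These bounds assume that every step takes its full allowance and that the event is submitted to the IRB. The stamp times are assumptions, since the documents give none. The finding is a weakness in a design choice, not a breach of the protocol's own rules, and it changes no estimate, test or decision rule. It merits action because weekly dosing continues at the other sites and the remedy is inexpensive.

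**What to change.** In Section 17.3, replace the 30-day limit with a requirement that MSK inform all participating sites of these SAEs within 5 calendar days of the MSK PI becoming aware, without waiting for the IRB stamp. Forward the stamped report when it arrives, as follow-up. Leave the 24-hour rule for deaths unchanged.

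For an event at a participating site, the latest notice would then be 3 + 5 = 8 days after that site learns of it; for one known first at MSK, 5 days after PI awareness. Starting the clock at awareness also removes the dependence on an undefined stamp date and on whether IRB submission is required.

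The cost is one sentence in the protocol and an e-mail to the sites based on the report already prepared for the manufacturer. The downside is that some early notices will need correction once review is complete. No dose, schedule or stopping rule is touched.

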17.5 Safety Reports

MSK must submit external safety reports to the MSK IRB/PB according to institutional guidelines. All external safety reports will be made available to the participating sites. For those safety reports that require an amendment, the participating sites will receive a special alert.

Participating sites are responsible for submitting safety reports to their local IRB per their local IRB guidelines. All local IRB approvals/acknowledgments of safety reports must be sent to MSK upon receipt.

18.0 INFORMED CONSENT PROCEDURES

Before protocol-specified procedures are carried out, consenting professionals will explain full details of the protocol and study procedures as well as the risks involved to participants prior to their inclusion in the study. Participants will also be informed that they are free to withdraw from the study at any time. All participants must sign an IRB/PB-approved consent form indicating their consent to participate. This consent form meets the requirements of the Code of Federal Regulations and the Institutional Review Board/Privacy Board of this Center. The consent form will include the following:

- 1. The nature and objectives, potential risks and benefits of the intended study.
- 2. The length of study and the likely follow-up required.
- 3. Alternatives to the proposed study. (This will include available standard and investigational therapies. In addition, patients will be offered an option of supportive care for therapeutic studies.)
- 4. The name of the investigator(s) responsible for the protocol.
- 5. The right of the participant to accept or refuse study interventions/interactions and to withdraw from participation at any time.

Before any protocol-specific procedures can be carried out, the consenting professional will fully explain the aspects of patient privacy concerning research specific information. In addition to signing the IRB Informed Consent, all patients must agree to the Research Authorization component of the informed consent form.

Each participant and consenting professional will sign the consent form. The participant must receive a copy of the signed informed consent form.

18.1 Informed Consent Procedures for Participating Sites

The investigators listed on the Consenting Professionals Lists at each participating site may obtain informed consent and care for the participants according to good clinical practice and protocol guidelines.

A note will be place in the medical record documenting that informed consent was obtained for this study, and that the participant acknowledges the risk of participation.

20.0 APPENDICES

Appendices will be stored in a separate file and will be submitted in electronic format.

Appendix A: Manuscript under editorial review

Appendix B: Romiplostim Product Information

Appendix C: Investigators Brochure
